### 5.3.5 Pharmacodynamic Parameters

Missing data for the pharmacodynamic parameters will be treated as such and no imputed values will be derived.

### 5.3.6 QTc

For the corrected QT (QTc) analyses, no values will be imputed for missing data.

## 5.4 Statistical Considerations of COVID-19 Impacted Data

In March 2020, the World Health Organization (WHO) announced a global pandemic of the virus SARS-CoV-2 and the resulting disease COVID-19. During the conduct of this trial, if any participant's data is impacted by this pandemic, the following considerations will be given in the data analyses:

- a) If a participant dropped out of the study during the DLT evaluation window in Part 1 due to COVID-19, a replacement participant may be added.
- b) Death caused by COVID-19 is still considered as an “event” in the analysis of PFS and OS. If deemed necessary, a sensitivity analysis may be performed where COVID-19 driven death is censored at the death date.
- c) If a scheduled tumor radiographic scan is delayed out of the [Schedule of Activity](#) allowable window, or is missing (i.e. participant skipped a scheduled tumor radiographic scan) due to any reasons related to the pandemic, this delay or missingness does not alter the censoring rules for PFS or TTP as described in [Appendix 1](#). A censoring reason of “COVID-19” may be added to the PFS or TTP summary if the specific reason of tumor scan delay or missing can be attributed to COVID-19. If deemed necessary, a sensitivity analysis may be performed where participants would be censored at the date of their last scan prior to their COVID-19 diagnosis.

In the confirmed ORR analysis, if a response can't be confirmed by a subsequent tumor scan because of the pandemic (i.e., the subsequent tumor scan wasn't performed), then the initial response will be considered as unconfirmed. No sensitivity analysis will be performed.

- d) Any COVID-19 related symptoms are to be captured as adverse events in the case report form. Those adverse events will be summarized in the same manner as other adverse events. If a label of COVID-19 can be identified in the investigator provided adverse event term, then a separate AE listing may be provided for just the COVID-19 related events.
- e) If identifiable, the COVID-19 related data points, including missing data where the reason of missing is identified as COVID-19 related (site closure hence data

could not be captured; participants skipped a visit because of concern over the pandemic), protocol deviations driven by COVID-19, safety events caused by COVID-19 may be separately listed.

## 6. ANALYSES AND SUMMARIES

### 6.1 Primary Endpoint(s)

#### 6.1.1 DLTs (Part 1)

Determination of MTD will be performed using Per-protocol analysis set (evaluable for MTD) as described above in [Section 3](#).

#### 6.1.2 Adverse Events (Part 1 and Part 2)

- Analysis set: Safety analysis set.
- Analysis methodology:

AEs will be characterized by type, frequency, severity (as graded by NCI CTCAE version 5.0, except CRS, which will be graded by ASTCT criteria (Lee et al., 2019)) timing, seriousness, and relationship to study therapy. Further description is given in Section 0. The primary focus will be on TEAEs. TEAEs is defined as any AE that occurs during the on-treatment period. AEs that occur after the on-treatment period may still be recorded in the clinical database and will be included in the AE listings, but will not be included in the on-treatment emergent AE summaries.

See Section 0 for details on the specific AE summaries to be provided.

- Missing data: If an AE start or stop date is missing, imputation will be performed. The imputed dates will be used to determine whether the AE is to be included in the TEAE summary. The missing AE start or stop dates will be listed as is in AE listings. When the CTCAE grade is missing for an AE, the AE will be excluded from the CTCAE grade summary table.

#### 6.1.3 Laboratory abnormalities (Part 1 and Part 2)

- Analysis methodology:

Laboratory abnormalities will be presented as tables and characterized by type, frequency, severity (as graded by NCI CTCAE version 5.0), and timing. For laboratory tests without CTCAE grade definitions, results will be categorized as normal, abnormal high/low, or not done. The number and percentage of participants who experienced laboratory test abnormalities will be summarized according to worst toxicity grade observed for each laboratory assay. Shift tables of baseline grade to worst post-baseline grade will be provided. Quantitative summaries for change from baseline and percent change from baseline for the laboratory tests may be provided, if deemed necessary. These summaries will be

presented for the entire on-treatment period and for the various subgroups of the study (by dose level for Part 1 and by expansion cohort for Part 2).

Hematology, serology and coagulation lab results can be combined into one summary output. Separate summaries will be created for chemistry tests. Urinalysis and pregnancy tests will not be summarized and will only be listed.

- Missing data: Missing lab values will not be imputed.

## 6.2 Secondary Endpoints

### Part 1 and Part 2

#### 6.2.1 irAEs

- Analysis methodology:

irAEs will be characterized by type, frequency, severity (as graded by NCI CTCAE version 5.0, except CRS, which will be graded by ASTCT criteria (Lee et al., 2019)) timing, seriousness, and relationship to study therapy. Further description is given in Section 0. irAEs that occur after the on-treatment period may still be recorded in the clinical database and will be included in the irAE listings, but will not be included in the on-treatment emergent AE summaries.

- Missing data: If an irAE start or stop date is missing, imputation will be performed. The imputed dates will be used to determine whether the irAE is to be included in the irTEAE summary. The missing irAE start or stop dates will be listed as is in irAE listings. When the CTCAE grade is missing for an irAE, the irAE will be excluded from the CTCAE grade summary table.

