07260437 administration during clinical visits may be resumed after agreement between investigator and sponsor.

- Participants should be observed for at least 1 hour post dose for all outpatient visits starting with C2D1 in both cohorts until the investigator has confirmed the participant has not exhibited signs of CRS (Table 7).
- Participants will undergo a telephone follow-up at 90 days (± 7 days) after the last dose of PF-07260437 to assess potential late irAEs. If any concern arises, the participant should be contacted for an in-person follow-up visit.

Dose escalation will continue until MTD has been reached (if an MTD is identified) and the RDE has been determined. At that time, if the dose escalation has reached the MTD and a priming dose has not been previously incorporated to the dose regimen, a priming dose escalation cohort to minimize C_{max} may be initiated based on clinical safety, PK/PD, and clinical efficacy. The same approach to priming as described above will be utilized. Priming dose escalation cohorts will continue until MTD with priming has been reached (if an MTD is identified) and the RDE with priming has been determined. Depending on emerging safety data, a 2 (or more) step-up priming dose approach may also be implemented as described above.

The DLT period for SC or IV dosing without priming will be 28 days. The DLT period with priming will extend to include the duration of the priming doses and 2 full doses after priming. (eg, if a priming dose is given on Day 1 and the first full dose on Day 15, the total DLT observation period will be 42 days). A traditional 2-parameter BLRM will be used to model the DLT relationship to the drug and inform dose escalation with or without priming. The maximum dose level increase will be 200% (dose tripling from the previous dose level).

Approximately 35 participants are expected to be enrolled into 1 of 5-7 sequential dose levels in Part 1 including at least 6 participants treated at the MTD. The actual number of participants enrolled will depend on the tolerability of PF-07260437 and the number of dose levels that are required to determine MTD/RDE.

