4.4. End of Study Definition

The end of the study is defined as 2 years from the last participant's first dose unless otherwise notified by the sponsor.

Accrual may be halted and a thorough safety analysis will be conducted and submitted to FDA in the event of significant safety concerns (eg, one Grade 5 SAE or two Grade 4 events considered at least possibly related to PF-07260437).

A participant is considered to have completed the study if he/she has completed all periods of the study, including the last scheduled procedure shown in the **SOA** which for Part 1 is the 4-week follow-up visit and for Part 2 is the OS follow-up.

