8.3.1. Time Period and Frequency for Collecting AE and SAE Information

The time period for actively eliciting and collecting AEs and SAEs (“active collection period”) for each participant begins from the time the participant provides informed consent, which is obtained before the participant’s participation in the study (ie, before undergoing any study-related procedure and/or receiving study intervention), through and including a minimum of 28 calendar days, except as indicated below, after the last administration of the study intervention.

Follow-up by the investigator continues throughout and after the active collection period and until the AE or SAE or its sequelae resolve or stabilize at a level acceptable to the investigator.

For participants who are screen failures, the active collection period ends when screen failure status is determined.

If the participant withdraws from the study and also withdraws consent for the collection of future information, the active collection period ends when consent is withdrawn.

If a participant permanently discontinues or temporarily discontinues study intervention because of an AE or SAE, the AE or SAE must be recorded on the CRF and the SAE reported using the CT SAE Report Form.

Investigators are not obligated to actively seek information on AEs or SAEs after the participant has concluded study participation. However, if the investigator learns of any SAE, including a death, at any time after a participant has completed the study, and he/she considers the event to be reasonably related to the study intervention, the investigator must promptly report the SAE to Pfizer using the CT SAE Report Form.

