### 3.5 Safety Endpoints

The on-treatment period will be used for all safety assessments. The on-treatment period is defined as the period that starts with the first dose of study treatment and ends at minimum (last dose of study treatment + 30 days, start of new anti-cancer therapy - 1 day).

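### irAEs with onset after the on-treatment period are listed but not tabulated, although the protocol schedules a 90-day contact to look for late irAEs

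*SAP*

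**What the plan says.** **Follow-up.** Protocol 4.1 states: "Participants will undergo a telephone follow-up at 90 days", with a window of ±7 days after the last dose, to assess possible late irAEs. The same section applies this to all participants. The contact appears in the Part 1 schedules without and with priming (Tables 1 and 3) and in the Part 2 schedule (Table 5).

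**Endpoint.** irAEs, described by type, frequency, severity, timing, seriousness and relationship, are a secondary endpoint in both parts (protocol Section 3; SAP 3.2). No time limit is given, and the estimand column reads N/A.

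**Analysis window.** SAP 3.5 says: "The on-treatment period will be used for all safety assessments". That period "ends at minimum (last dose of study treatment + 30 days, start of new anti-cancer therapy - 1 day". SAP 6.2.1 adds: "irAEs that occur after the on-treatment period may still be recorded in the clinical database"; such events "will be included in the irAE listings, but will not be included in the on-treatment emergent AE summaries". Onset date decides entry: "The imputed dates will be used to determine whether the irAE is to be included in the irTEAE summary".

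**Text pointing the other way.** SAP 3.5.1 and 6.6.1 say the AE summaries span the whole study and that irAEs are handled alike.

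**Collection.** Protocol 8.3.1 sets active AE collection at "a minimum of 28 calendar days, except as indicated below, after the last administration". Protocol 8.3.1.2 ends recording of nonserious AEs when new anticancer therapy starts. Protocol 4.4 names the last scheduled procedure for a completer, "which for Part 1 is the 4-week follow-up visit".

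**The concern.** The 90-day contact exists to find late immune toxicity, and irAE frequency, severity and timing form a secondary endpoint. Under the specific SAP rule, an irAE with onset after day 30 enters no frequency, grade or timing table, at any dose level or in any expansion cohort. A reader of the report would see an irAE incidence that stops at day 30 and would have to rebuild the later experience from listings.

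The listings are themselves uncertain. The SAP says late irAEs may be recorded, not that they must be. The protocol nowhere says outright that an irAE reported at the 90-day call goes on the CRF.

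**Working it through.** The plan gives no figure to reproduce. The check compares windows and then sets the conflicting sections side by side.

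**Inputs**
- Summary cut-off: day 30 after last dose (SAP 3.5). The AE estimand uses day 28 instead (SAP 2.1.1; protocol 9.1.1.1).
- Contact: day 90, window day 83 to day 97 (protocol 4.1).

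**Formulae:** gap = contact day − cut-off; share = gap ÷ contact day.

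| Cut-off | Contact day 83 | Contact day 90 | Contact day 97 |
|---|---|---|---|
| Day 30 (SAP 3.5) | 53/83 = 64% | 60/90 = 67% | 67/97 = 69% |
| Day 28 (estimand) | 55/83 = 66% | 62/90 = 69% | 69/97 = 71% |

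For anyone who starts new anticancer therapy before the cut-off, the period ends sooner and the gap is longer.

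**Which events fall out**
- Onset by day 30 and before new anticancer therapy, first reported at the contact: tabulated.
- Onset after day 30, or on or after the start of new anticancer therapy: listed if recorded, not tabulated.

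**Number of events.** No late-irAE rate is given, so this cannot be calculated. For scale only, assume a proportion q of participants have an irAE with onset in the excluded window. In a cohort of 20, the expected number is 20q, and the chance of at least one is 1 − (1 − q)^20:
- q = 5%: 1 participant, 64%
- q = 10%: 2 participants, 88%
- q = 20%: 4 participants, 99%

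These values of q are assumptions, not estimates.

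**SAP against SAP.** Section 3.5 applies the on-treatment period to every safety assessment, and 6.2.1 repeats the limit for irAEs. Section 3.5.1, which sits under 3.5, and 6.6.1 describe whole-study summaries and extend that to irAEs. A programmer could build either table. Section 6.2.1 is the rule specific to this endpoint, so I take it as the operative one.

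**Protocol against protocol.** Section 4.4 makes the 4-week visit the last scheduled Part 1 procedure. Tables 1 and 3 show the 90-day contact after it. Both cannot be right.

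**The case against.** The strongest reply has four parts.

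1. **Late events are still reported.** They appear in listings, and with about 35 participants in Part 1 and 20 per Part 2 cohort, single events stay visible. Protocol 4.3.7 also sends late toxicities to dose-level review, and those meeting the DLT definition count towards the MTD, RDE and RP2D. This stands. It limits the consequence to the endpoint's tables; dose decisions are not cut off from late toxicity.
2. **The SAP may already intend whole-study summaries** (3.5.1, 6.6.1). This stands in part. It makes the matter an inconsistency as well as an exclusion, but it does not settle it, because 3.5 and 6.2.1 say the opposite and 6.2.1 is more specific.
3. **An on-treatment incidence is a legitimate quantity.** True. With the irAE estimand marked N/A, no longer target period is stated, so calling the planned figure biased goes too far. What can be said is that it does not describe irAEs up to the contact, and that incidence to the contact cannot be lower.
4. **Residual exposure is a weak argument.** With the projected half-life of 15 days (protocol 2.2.2), 0.5^(30/15) = 25% of drug remains at day 30 and 0.5^(90/15) = 1.6% at day 90. The half-life is a projection and exposure is nearly gone by the contact. I do not rest the point on it.

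Two stronger readings are tempting and unsupported. A reader might infer that everything found at the 90-day contact is excluded, so that the contact adds nothing to any table; the rule turns on onset date, not on when the event is reported. A reader might also infer that protocol 8.3.1 contradicts the schedule; its 28 days are a minimum, so longer collection is allowed, and its statement that investigators need not seek AEs applies only once participation has ended. The clear conflict is the Part 1 clause in 4.4.

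**Conclusion.** The point holds in this form: under SAP 3.5 and 6.2.1, irAEs with onset after last dose + 30 days, or from the start of new anticancer therapy if earlier, are left out of the irAE summaries of a secondary endpoint, while the protocol schedules a contact for every participant to look for them. The excluded onset window is about two thirds of the time from last dose to contact. The effect on incidence is unknown.

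This rests on reading 6.2.1 as the operative rule over 3.5.1 and 6.6.1. If the whole-study wording was intended, the defect is instead that the SAP contradicts itself on the window. Either way the text needs changing before the tables are programmed. The change should be made, but nothing here threatens the trial's primary objectives.

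**What to change.** 1. **SAP 6.2.1:** keep the on-treatment irAE table. Add one table of irAE incidence by worst grade, by dose level (Part 1) or cohort (Part 2), from first dose to the 90-day contact (last dose + 90 days, up to 97).
2. **New anticancer therapy:** stop the main version of that table on the day before new therapy, because nonserious AE recording ends when it starts and later events may reflect the new treatment. Label any version running past that point as limited by protocol 8.3.1.2.
3. **SAP 3.5 and 6.2.1 against 3.5.1 and 6.6.1:** state one window for each table. Settle the 28-day and 30-day cut-offs at the same time.
4. **Protocol 8.3.1 and 8.3.1.2:** state that irAEs reported at the 90-day contact are recorded on the CRF, with onset date and grade.
5. **Protocol 4.4:** make the 90-day contact the last Part 1 procedure, in line with Tables 1 and 3.

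The cost is one more table, wording changes in both documents, and slightly more AE recording at a call already scheduled.

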#### 6.2.2 Single-Dose and Steady-State PF-07260437 Pharmacokinetic Analysis

- Analysis set: PK analysis set

Serum concentrations of PF-07260437 will be summarized descriptively (n, mean, standard deviation, coefficient of variation, median, minimum, maximum, geometric mean, and its associated coefficient of variation) by dose, cycle, day, and nominal time.

Individual participant serum concentration-time data within a dose interval after Cycle 1 Day 1 and Cycle 2 Day 1 will be analyzed using noncompartmental methods to determine single and multiple dose PK parameters.

Single dose PK parameters to be estimated will include the serum  $C_{\max}$ ,  $T_{\max}$  and  $AUC_{\text{last}}$ , and as data permit,  $AUC$  from time 0 extrapolated to infinity ( $AUC_{\text{inf}}$ ),  $t_{1/2}$ , clearance ( $CL/F$  for SC dosing and  $CL$  for IV dosing) and volume ( $V_z/F$  for SC dosing and  $V_{ss}$  for IV dosing).

Multiple dose PK parameters to be estimated will include  $C_{\max,ss}$ ,  $T_{\max,ss}$ ,  $AUC_{ss,\tau}$ ,  $C_{\min,ss}$ , clearance ( $CL_{ss}/F$  for SC and  $CL_{ss}$  for IV) and as data permit, volume ( $V_z/F$  for SC or  $V_{ss}$  for IV),  $t_{1/2}$ , and  $R_{ac}$  ( $AUC_{ss,\tau}/AUC_{sd,\tau}$ ). The single dose and steady-state PK parameters will be

summarized descriptively (n, mean, standard deviation, coefficient of variation, median, minimum, maximum, geometric mean, and its associated coefficient of variation) by dose level and cycle.

Dose normalized  $AUC_{\text{inf}}$  ( $AUC_{\tau}$  at steady state) and  $C_{\text{max}}$  will be plotted against dose (using a logarithmic scale) by cycle. These plots will include individual participant values and the geometric means for each dose.

### 6.2.3 Analysis of Immunogenicity Data

For the immunogenicity data, the percentage of participants with positive ADA and neutralizing antibodies each will be summarized. For participants with positive ADA or neutralizing antibodies, the magnitude (titer), time of onset, and duration of ADA or neutralizing antibodies response will also be described, if data permit.

## Part 2

### 6.2.4 Efficacy Analysis

Response Evaluable Set will be used for all response-related analyses including ORR, DoR, PFS, and TTP (RECIST, irRECIST). Tumor response will be presented in the form of participant data listings that include, but are not limited to tumor type, tumor response at each visit, and best overall response. Immune related response by irRECIST will be calculated and reported similarly to RECIST response. OS will be reported on the Full Analysis Set as well as on the mITT.

Data will be summarized (also graphically where appropriate) and listed by expansion cohort.

- **Overall Response Rate (ORR)**

- Overall response rate (ORR) is defined as the proportion of patients with a BOR of confirmed CR or confirmed PR by Investigator assessment in intracranial metastasis and extracranial lesions per mRECIST v1.1 (or RANO for glioblastomas) and RECIST v1.1, respectively.

- **Duration of Response (DOR)**

- Duration of response is defined as the time from start date (which is the date of first documentation of PR or CR) to date of first documentation of objective progression or death. Both confirmed DOR and unconfirmed DOR (uDOR) will be determined and reported separately for the subset of participants with a confirmed and unconfirmed objective response of CR or PR (defined below). DOR will be derived for Intracranial/RANO response rate, extracranial response rate and ORR.

- **Best Overall Response (BOR)**

- **Complete Response (CR):** Two objective statuses of CR a minimum of 4 weeks apart documented before PD.
- **Partial Response (PR):** Two objective statuses of PR or better (PR followed by PR or PR followed by CR) a minimum of 4 weeks apart documented before PD, but not qualifying as CR. Sequences of PR- Stable- PR are considered PRs as long as the two PR responses are observed at a minimum of 4 weeks apart.
- **Stable Disease (SD) (applicable only to patients with measurable disease at baseline):** At least one objective status of stable disease or better documented at least 6 weeks after start of treatment and before PD but not qualifying as CR or PR.
- **Non-CR/non-PD (applicable only to patients with non-measurable disease at baseline):** at least one non-CR/non-PD assessment (or better) documented at least 5 weeks after start of treatment and before first documentation of PD (and not qualifying for CR or PR).
- **Progressive Disease (PD):** Progression documented within 12 weeks after 'start date' and not qualifying as CR, PR or SD.
- **Not Evaluable (NE):** All other cases. Note that reasons for NE should be summarized and the following reasons could be used:
  - No adequate baseline assessment
  - No evidence of disease at baseline
  - No post-baseline assessments due to early death, i.e., death prior to 6 weeks after 'start date'.
  - No post-baseline assessments due to other reasons
  - All post-baseline assessments have overall response NE
  - New anti-cancer therapy started before first post-baseline assessment
  - SD of insufficient duration (<5 weeks after 'start date' without further evaluable tumor assessments)
  - PD too late (>12 weeks after start of treatment)
  - Special and rare cases where BOR is NE due to both SD of insufficient duration ('too early') and late PD will be classified as 'SD of insufficient duration.'

- Unconfirmed CR (uCR) is defined as one objective status of CR documented before PD.
- Unconfirmed PR (uPR) is defined as one objective status of PR documented before PD but not qualifying as uCR.

Note: An objective status of PR, SD, or Non-CR/Non-PD cannot follow one of CR. SD can follow PR only in the rare case that tumor increases by less than 20% from the nadir, but enough that a previously documented 30% decrease from baseline no longer holds. If this occurs the sequence PR – SD – PR is considered a confirmed PR. A sequence of PR – SD – SD – PD would be a best response of SD if the window for SD definition has been met.

Patients with a BOR of “Not Evaluable” (NE) based on confirmed responses will be summarized by reason for having unknown status. The following reasons will be used:

- No adequate baseline assessment.
- No post-baseline assessments due to early death .
- No post-baseline assessments due to COVID-19 (ie, patients miss tumor assessment visits due to COVID-19 pandemic).
- No post-baseline assessments due to other reasons.
- All post-baseline assessments have overall response NE.
- New anticancer therapy started before first post-baseline assessment.
- SD of insufficient duration (<6 weeks after date of the first dose without further evaluable tumor assessments).
- PD >12 weeks after date of the first dose (ie, tumor assessment of PD was >12 weeks after date of the first dose and there was no tumor assessment in between).

Special and rare cases where BOR is NE due to both SD of insufficient duration (SD <6 weeks after date of the first dose) and late PD (PD >12 weeks after date of the first dose) will be classified as “SD of insufficient duration”.

- Tumor response will be presented in the form of participants data listings that include, but are not limited to: tumor type, actual received day 1 dose, tumor response at each assessment, and best overall response. Progression date, death date, date of first response, last assessment date, and date of last contact will also be listed. Additionally, a graphical representation (swimmer plot) will be provided to display tumor response overtime and a waterfall plot displaying the best percentage change in tumor size will be provided.
- Missing data: Data after the study intervention is discontinued and rescue will be excluded; intermediate missing values (ie, values collected between baseline and the last study measurement) will not be imputed.

